5.8. Concomitant Treatment(s)

5.8.1. Prohibited Medications

5.8.1.1. Medications Prohibited through Week 80

The following medications are prohibited from the time period specified until Week 80 or the final Early Termination Visit.

- Biologics (Refer to [Appendix 4](#)) other than investigational product (eg, TNF- α inhibitors such as adalimumab, etanercept, infliximab), including any live vaccines, within 3 months of the IPAP or during the study.
- Systemic corticosteroid therapy within 30 days prior to Screening (inhaled and topical corticosteroids are permitted).
- Local or epidural injection of corticosteroids, as well as injections of corticosteroids in the facet joint or elsewhere in the back within 3 months prior to Screening.

5.8.1.2. Medications Prohibited During Entire Treatment Period through Week 64

In addition to the prohibited medications listed in Section 5.8.1.1, the following medications are prohibited from the time period specified through Week 64:

- Aspirin at doses >324 mg/day or salicylate containing medications.

- Opioid analgesics are prohibited beginning 48 hours prior to the start of the IPAP through Week 64.

As specified in Section 5.8.2, occasional use of medication to relieve pain is permitted in certain situations. Use of NSAIDs and COX-2 selective inhibitors (outside of oral investigational product), both prescription or over-the-counter (OTC) is prohibited through the Week 64 visit.

Using IRT, subjects will record the number of days of concomitant NSAID use weekly from Baseline (Day 1) through the Week 80 visit. Additional information regarding NSAID use such as medication names, dosage and reason for use will be collected by the site on a CRF. Subjects who report concomitant use of prescription or OTC NSAIDs during the study will be managed as per the following guidelines:

- Subjects who report concomitant use of NSAID should be interviewed by study site personnel to determine reason for use and if the subject anticipates being able to comply with concomitant medication restrictions in the future. Subjects who indicate they are taking NSAIDs because of insufficient chronic low back pain relief or who indicate that they cannot or will not be able to comply with concomitant medication restrictions will be withdrawn from investigational product and entered in the Early Termination Follow-up period (Refer to Section 6.9).

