- At the discretion of the investigator, standard of care treatments for chronic low back pain may be initiated for subjects who have completed the Week 64 visit or for subjects who have prematurely discontinued investigational product provided 16 weeks have elapsed since the last dose of SC investigational product. In this study, standard of care treatment refers to analgesics or other treatments approved by MHLW and generally considered effective therapy for chronic low back pain. These medications include but are not limited to opioids, topical analgesics, NSAIDs, coxibs, tapentadol, tricyclic anti-depressants, benzodiazepines, or tramadol, and are prescribed at the discretion of

the investigator. Standard of care treatments are not considered investigational product but the cost of pre-specified analgesics will be paid for by Pfizer while the subject is participating in the Follow-up Period. Their use will be recorded on the concomitant medication CRF.

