5.9. Rescue Therapy

Subjects will be provided with rescue medication (acetaminophen/paracetamol tablets).

During the Washout Period and the IPAP (ie, prior to Baseline [Randomization]), subjects may take rescue medication as needed up to a maximum daily dose of 3000 mg per day. Rescue medication must be discontinued 24 hours prior to the Baseline (Randomization) visit.

In the event of inadequate pain relief for chronic low back pain during the double-blind treatment period beginning at the Baseline (Randomization) visit through Week 16, Subjects may take acetaminophen/paracetamol up to 3 days per week up to a maximum daily dose of 3000 mg per day. Subjects must discontinue rescue medication within 24 hours of any scheduled site visit prior to any scheduled study visit at which efficacy data is collected (ie, up to the Week 64 visit that occurs 16 weeks after the last dose of SC investigational product).

From the Baseline (Randomization) visit through Week 16, subjects taking greater than 3 days per week of rescue medication (any level of acetaminophen/paracetamol used specifically for chronic low back pain) must be interviewed by study site personnel to determine if this is due to lack of efficacy or other reasons, and the discussion should be noted in the subject's records. Up to Week 16, subjects who have taken rescue medication more frequently than specified in the protocol and indicate that they cannot or will not follow the rescue medication protocol requirements because of insufficient pain relief for chronic low back pain should be withdrawn from investigational product and entered in the Early Termination Follow-up Period (See Section 6.9.1). Subjects who indicate that they anticipate being able to take rescue medication no more than 3 days per week going forward will be allowed to remain in the study. However, if these subjects continue to take rescue medication more than 3 days per week, they should be withdrawn from investigational product.

After the Week 16 visit, subjects may take acetaminophen/paracetamol rescue medication daily, up to the maximum permitted dose of 3000 mg per day. After Week 64, subjects may be started on standard of care treatments for low back pain. After Week 64, subjects may continue to use acetaminophen/paracetamol as needed up to the maximum dose per day as permitted by national labeling.

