Up to 16 weeks after the last dose of SC investigational product, subjects who discontinue treatment and enter the Early Termination Follow-up Period may take acetaminophen/paracetamol rescue medication daily up to the maximum permitted dose of 3000 mg per day. After the second Early Termination Follow-up visit occurring approximately 16 weeks after the last SC dose of investigational product, subjects may be

started on standard of care treatments for low back pain. After the second Early Termination Follow-up visit, subjects may continue to use acetaminophen/paracetamol as needed up to the maximum dose per day as permitted by national labeling.

Subjects should return rescue medication bottles at each study visit for assessment of compliance.

Subjects will be instructed that many OTC medications contain acetaminophen/paracetamol, and to guard against overuse. Subjects will be instructed to keep a daily record of their acetaminophen/paracetamol rescue medication usage via the IRT through Week 16. After Week 16 and through the Week 80 visit, usage of acetaminophen/paracetamol rescue medication will be recorded once weekly via the IRT. Subjects must discontinue rescue medication within 24 hours of any scheduled site visit prior to any scheduled study visit at which efficacy data is collected (ie, up to the Week 64 visit that occurs 16 weeks after the last dose of SC investigational product). Use of acetaminophen/paracetamol for other types of pain or illness during the study (eg, toothache, headache, fever) should be recorded as a concomitant medication on the appropriate CRF page.

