6. STUDY PROCEDURES

Refer to Schedule of Activities ([Table 1](#) and [Table 2](#)) for the lists of procedures to be performed throughout the study.

If possible, each subject's clinic visit should be conducted at approximately the same time of day throughout their participation in the study. As a general rule, scales/instruments should be completed first by the subject upon arrival at the clinic and vital signs should be assessed prior to blood draws at non-dosing visits.

The study visit windows are ± 2 days for the visit at Week 2 and ± 3 days for the visit at Week 4. The study visit windows are ± 7 days for the clinic visits at Weeks 8, 16, 24, 32, 40, 48 and 56 and for the visits during the Follow-up Period and for the Early Termination Visits. The study visit windows are ± 7 days for the telephone visits at Weeks 12, 20, 28, 36, 44, 52, 60, 68, 72, 76 and during the Early Termination Follow-up. Study visits should be scheduled with reference to the original baseline visit date as much as possible. Subject scheduling issues should be brought to the attention of the study monitor for resolution. Dosing visits should occur no earlier than 7 weeks from the previous injection. The Week 24 X-rays may be obtained up to 30 days before the Week 24 visit, but must be completed and read by the Central Reader before the Week 24 dose of SC investigational product is administered. The visit window for the Week 56 X-rays is ± 30 days from the nominal time point of the visit. The window for the Week 80 X-rays is ± 30 days of the nominal time of the visit but should be obtained as close as possible to the Week 80 visit, and preferably no more than 14 days after the Week 80 visit.

Subjects will be reminded to abstain from taking rescue medication 24 hours prior to any study visit at which efficacy data is collected.

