6.7. Weeks 68, 72, and 76 Telephone Visits

The subject will be contacted by telephone at Week 68, 72 and 76 to review adverse events, concomitant medications and compliance with weekly IRT entries.

Refer to Schedule of Activities [Table 2](#) for the procedures to be performed at the Week 68, 72 and 76 Telephone Contacts.

Week 76: Verify that follow-up radiographs required for the Week 80 visit have been scheduled and will be completed (refer to Section [7.3.8](#)).

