7.4.1. Dysesthesia/Allodynia

Transient, resolved dysesthesia/allodynia: Administer SC investigational product as planned as long as the condition has resolved before the next scheduled dose of investigational product.

Unresolved dysesthesia/allodynia: Withhold the SC investigational product for a maximum of 14 days beyond the planned dosing day to allow for resolution of the adverse event. If the dysesthesia/allodynia has not resolved within the 14-day period after the scheduled dosing

date, the subject will not receive any additional doses of investigational product and will enter the Early Termination Follow-up Period (see Section 6.9).

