bradycardia), syncope, orthostatic hypotension (as described above and in boxes C and E of flow diagram [Figure 6](#)), anhidrosis or hypohidrosis should be further evaluated for the presence of sympathetic autonomic neuropathy by a cardiologist or neurologist as soon as possible.

The investigator should determine the appropriate type of consultation (neurology or cardiology) depending on the subject's symptom presentation and the investigator's assessment as to the specialist best able to evaluate the subject. Pfizer will provide a guidance document which outlines appropriate recommendations regarding tests to consider for subject work-up.

These subjects should not be dosed with SC investigational product until the absence of sympathetic autonomic neuropathy has been confirmed. Subjects who are not deemed to have a sympathetic autonomic neuropathy based on this evaluation can continue the study provided no more than 12 weeks have elapsed since the last dose of SC treatment (Boxes H and K of flow diagram [Figure 6](#)). However, if the subject is still symptomatic with bradycardia, syncope, orthostatic hypotension, anhidrosis or hypohidrosis up to 12 weeks after the last dose of SC treatment, he/she should not receive additional investigational product; even if a sympathetic autonomic neuropathy has not been confirmed (Boxes J and L of flow diagram [Figure 6](#)), and will enter the Early Termination Follow-up Period (refer to [Section 6.9](#)). Subjects found to have a sympathetic autonomic neuropathy (Boxes I and L of flow diagram [Figure 6](#)), should not receive additional investigational product and will enter the Early Termination Follow-up Period (see [Section 6.9](#)).

Figure 6. Follow-up Procedures for Confirmed Orthostatic Hypotension Events

OH=Orthostatic Hypotension

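### After a delayed seventh injection, main-study completers may start NSAIDs or standard of care at a baseline-timed Week 64 visit that falls less than 16 weeks after the last dose

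*Protocol*

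**What the plan says.** - **NSAID ban (Protocol 5.8.1.2).** "Use of NSAIDs and COX-2 selective inhibitors (outside of oral investigational product), both prescription or over-the-counter (OTC) is prohibited through the Week 64 visit". No condition on time since the last injection is attached.
- **Standard of care (5.8.2).** It "may be initiated for subjects who have completed the Week 64 visit or for subjects who have prematurely discontinued investigational product provided 16 weeks" have passed since the last subcutaneous (SC) dose. The treatments listed there include NSAIDs and coxibs.
- **Rescue therapy (5.9).** "After Week 64, subjects may be started on standard of care treatments for low back pain", again without a time-since-dose condition. The same section describes efficacy collection as running "up to the Week 64 visit that occurs 16 weeks after the last dose of SC investigational product". That describes the visit; it does not restrict treatment.
- **Schedule (Table 2).** Standard-of-care assignment is listed at Week 64 (Day 449 ±7) and at Early Termination (ET) Visit 2 (16 weeks after the last dose, ±7 days).
- **Visit timing (section 6).** "Study visits should be scheduled with reference to the original baseline visit date as much as possible".
- **Permitted dose delays.** Section 6 gives dosing visits a ±7-day window. For unresolved dysesthesia or allodynia, 7.4.1 says: "Withhold the SC investigational product for a maximum of 14 days beyond the planned dosing day". After a negative work-up for sympathetic neuropathy, 7.4.3 says the subject "can continue the study provided no more than 12 weeks have elapsed since the last dose of SC treatment".

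**The concern.** Sixteen weeks from the last injection is an interval that the sponsor uses repeatedly. It appears in the 5.8.2 proviso, in the substudy's advice on chronic NSAID use (Appendix 18, 105.1), and in the SAP's split of concomitant medication (6.5.4). For main-study completers the interval is replaced by a calendar visit, which is equivalent only if the seventh dose is on time.

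What is at stake is a joint-safety precaution. Section 1.2.4.5 lists exclusion of chronic concomitant NSAID use first among the risk-minimization measures. It reports a much lower risk of rapidly progressive osteoarthritis with tanezumab alone than with tanezumab plus an NSAID. Subjects enter on a regular NSAID and stop oral study product at Week 56, so a return to NSAIDs as soon as the ban lifts is foreseeable.

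**Working it through.** **Inputs.** The nominal days are Week 40 (sixth dose) = Day 281, Week 48 (seventh dose) = Day 337 and Week 64 = Day 449 (SAP Appendix 2.1; Protocol Table 2 for Week 64). The ±7-day windows come from Protocol section 6. The 14-day hold is in 7.4.1 and the 12-week (84-day) limit in 7.4.3.

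**The plan's own figure.** 449 − 337 = 112 days = 16 weeks, so the description in 5.9 is exact on the nominal schedule.

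**Formula.** Gap = day of Week 64 visit − actual day of seventh dose.

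| Case | Seventh dose | Week 64 on time (Day 449) | Week 64 early (Day 442) |
|---|---|---|---|
| On schedule | 337 | 112 | 105 |
| Dose at +7 | 344 | 105 | 98 |
| 14-day hold from Day 337 | 351 | 98 | 91 |
| 14-day hold from Day 344 | 358 | 91 | 84 |
| 12-week rule, sixth dose Day 281 | 281 + 84 = 365 | 84 | 77 |
| 12-week rule, sixth dose Day 288 | 288 + 84 = 372 | 77 | 70 |

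The fourth row assumes that the planned dosing day from which the hold runs can itself be a window day. If it must be Day 337, the hold gives 91 to 98. A late Week 64 visit adds 7 days to any row. Stacked delays go lower: a sixth dose held to Day 295, then the full 84 days, puts the seventh dose on Day 379, and 442 − 379 = 63.

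**Shortfall against 112 days.** Windows alone: 112 − 105 = 7 to 112 − 98 = 14 days. 14-day hold: 112 − 98 = 14 to 112 − 84 = 28 days. 12-week rule: 112 − 84 = 28 to 112 − 70 = 42 days.

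**Comparison with early terminators.** ET Visit 2 at the early edge of its window is on day 112 − 7 = 105 after the last dose. One week of tolerance is therefore common to both groups.

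**Residual drug, rough guide only.** Protocol 1.2.4.6 gives half-lives between 12.5 and 24 days. Simple decay, 2^(−days/half-life), leaves 0.2–3.9% at 112 days, 0.4–5.9% at 98 days and 2.1–13.2% at 70 days. This ignores the 10 to 12 days to peak after SC injection, so only the comparison is useful: little changes at 98 days, more at 70.

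**How many subjects.** The documents do not say how many seventh doses will be late. Protocol Table 6 implies 38 to 78 tanezumab completers in this study, and only those with a late seventh dose are exposed to the gap.

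**The case against.** Several objections have force.

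- **Intent is plain and sites have latitude.** Section 5.9 says that Week 64 is 16 weeks after the last dose. Section 6 anchors visits to Baseline only as far as possible and sends scheduling problems to the monitor. A site with a held dose can move Week 64, so the shortfall is permitted, not required. This stands, but it leaves a safety interval to site initiative.
- **The 5.8.2 proviso might cover completers.** Its position favours early discontinuers only. Even on the wider reading, 5.8.1.2 and 5.9 carry no such condition, so the text would still conflict.
- **Early terminators are not held to a strict floor.** A reader might infer from 5.8.2 that an early terminator can never start before 16 weeks while a completer can. The documents do not support that contrast. Sections 5.9 and 6.9 release early terminators after a visit at approximately 16 weeks, and Table 2 gives that visit ±7 days. The 105-day completer case is therefore no anomaly.
- **Sixteen weeks is not shown to be a hard NSAID threshold.** The substudy prohibits no medication and only advises avoiding chronic NSAIDs if possible. Section 6.9 also links the start of standard of care to completion of efficacy assessments.
- **Harm is inferred.** Section 1.2.4.5 concerns combination therapy. It gives nothing on NSAIDs begun 10 to 14 weeks after a last dose, and notes that most affected subjects had advanced osteoarthritis in the joint, which eligibility here is designed to exclude. Weekly NSAID and joint-pain reporting and the Week 80 X-rays continue.

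These points shrink the concern. They do not supply the missing rule for a held dose.

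**Conclusion.** The point holds as a minor design matter. Followed literally, the completer rule can undercut the protocol's own 16-week interval. The material cases are a 14-day hold (about 84 to 98 days with Week 64 on time or early) and, rarely, the 12-week rule (70 to 84 days). The visit-window case of 98 days needs a late dose and an early visit together, and is small.

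This rests on two assumptions: that Week 64 stays tied to Baseline after a late dose, and that 7.4.3 allows the full 12 weeks before the seventh dose. The second is an inference, because 7.4.3 does not discuss later visits. No endpoint or planned analysis is affected.

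A reader might also infer a contraception gap, since the last scheduled reminder is at Week 64. That does not follow: Protocol 4.4 already ties the duty to 112 days after the last SC dose, whatever the visit calendar.

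**What to change.** In Protocol 5.8.1.2, 5.8.2 and 5.9, state that NSAIDs and standard of care may start only after the Week 64 visit (or ET Visit 2) and once at least 16 weeks have elapsed since the last dose of SC investigational product. Apply this in all three arms so that the waiting rule does not reveal treatment. It also removes the mismatch between the 5.8.2 proviso and the visit-based wording for early terminators.

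The cost is one clause in three places, with no new visit, test or procedure. Late-dosed subjects usually wait about one to three weeks longer. The wait is four weeks if a 14-day hold starts from a late dosing day and Week 64 is early, and rarely up to six weeks under the 12-week rule. Acetaminophen remains available.

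The burden also falls on celecoxib subjects, who have no tanezumab-related reason to wait and whose oral product ends at Week 56 (Day 393). Their NSAID-free time is 449 − 393 = 56 days on schedule. With the latest seventh dose tabulated (Day 372), it would be (372 + 112) − 393 = 91 days. That is the real downside, and it is confined to a few subjects.

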5.8.1.4. Prohibited Non-pharmacological Therapies

To investigate the response criteria (see Sections 3 and 6.4.5), initiation of non-pharmacological therapies is prohibited through Week 16.

- Commencing of physiotherapy is not allowed from the beginning of the IPAP through Week 16. This involves the requirement for new, concomitant physiotherapy including, but not limited to, transdermal electroneural stimulation (TENS), physical therapy, massage, acupuncture, and spinal manipulation. If the subject has had physiotherapy regularly for at least 4 weeks prior to Screening, the subject may participate in the study

but should maintain this therapy at least through Week 16. Facet joint injections and nerve blocks are prohibited beginning 30 days prior to IPAP and through Week 64.

5.8.2. Permitted Medications

Medications for other (non-chronic low back pain, non-pain) conditions are permitted provided the subject has received a stable dose for at least 30 days before the IPAP (30 days prior to Screening for antihypertensive medications) and the dose is not expected to change during the study. Note however, that dose adjustments (including starting a new therapy) during the study can be made if required, and recorded on the concomitant medication CRF. Subjects taking cytochrome (CYP3A4/5) enzyme inducers (eg, carbamazepine and rifampin) should be advised that these agents may interfere with the efficacy of hormonal contraceptive products.

- Occasional use of pain medications for pain is permitted in situations such as outpatient diagnostic procedures (eg, colonoscopy, dental procedures) or limited accidental injury (eg, ankle sprains, minor fractures, minor burns/sunburns). The subject should be counseled to avoid scheduling prospective procedures such that pain medications would be needed within 48 hours of a study visit. Contact the study monitor for guidance/approval regarding the use of prohibited medications for other self-limiting conditions, accidental injury or other surgical procedures as the extent of the condition, injury or procedure and the resulting pain medication usage may require termination from the study.
- Low-dose aspirin therapy for cardiac prophylaxis (≤ 324 mg per day).
- After the Week 16 visit, subjects may initiate skeletal muscle relaxants, pregabalin, gabapentin, benzodiazepines, sedative/hypnotics, anxiolytics and anti-depressants, herbal, homeopathic, and naturopathic remedies and topical analgesics (except for NSAIDs and Opioids [eg, Fentanyl and Buprenorphine]). However, the analgesics for chronic low back pain (NSAIDs and opioids, Refer to [Appendix 4](#)) except investigational product (tanezumab and celecoxib) are prohibited through Week 64. Subjects should be counseled to consult with the study site before initiating any new therapy and investigators should evaluate any new therapy for potential adverse interactions with celecoxib or rescue therapy by consulting the product labeling. Furthermore, subjects who have taken a stable dose of these products for at least 30 days prior to Screening will be allowed to continue their regimen.
- At the discretion of the investigator, standard of care treatments for chronic low back pain may be initiated for subjects who have completed the Week 64 visit or for subjects who have prematurely discontinued investigational product provided 16 weeks have elapsed since the last dose of SC investigational product. In this study, standard of care treatment refers to analgesics or other treatments approved by MHLW and generally considered effective therapy for chronic low back pain. These medications include but are not limited to opioids, topical analgesics, NSAIDs, coxibs, tapentadol, tricyclic anti-depressants, benzodiazepines, or tramadol, and are prescribed at the discretion of

the investigator. Standard of care treatments are not considered investigational product but the cost of pre-specified analgesics will be paid for by Pfizer while the subject is participating in the Follow-up Period. Their use will be recorded on the concomitant medication CRF.

